1.1 Study rationale

The goal of the ECLIPSE project is to develop novel devices that are capable to identify pathogens; the new diagnostic tools should be reliable and accurate, but also portable, rapid, inexpensive, and easy-to-use to allow their employment as screening tests. In this study we propose an initial evaluation of new platforms that will be developed within the ECLIPSE project, these novel platforms will combine interdisciplinary elements as follows:

- 1) the use of electrochemiluminescence (ECL) as a highly sensitive transduction mechanism for the realization of easy-to-use, portable and inexpensive devices;
- 2) the development of nano- and biotechnological structures to increase sensitivity by signal amplification;
- 3) the development of recognition strategies that offer high affinity and selectivity, thus leading to high reliability.

The platforms developed within the ECLIPSE project exhibit the potential to become a game changer in European countries, becoming a cornerstone for rapid testing and reliable diagnosis of infections; these newly developed platforms are expected to overcome the current limitations of molecular testing (high cost, time required and need for well-equipped laboratories) and rapid testing (high number of false-negative results). In addition, the newly developed platforms may have important applications in low-income countries, countries that will benefit from a simple and inexpensive approach to detect the many infectious diseases that affect millions of people each year.

1.2.1 Extent and evaluation of current knowledge directly linked to the scientific question(s) to be answered by the clinical study

The recent COVID-19 pandemic has revealed the need to develop tests that are accurate, rapid, and inexpensive for the diagnosis of infectious diseases. This problem is relevant not only for viruses, but also for bacteria and parasites: the identification of pathogens at very low concentrations by simple and accurate methods is still largely unsatisfied because these microorganisms are structurally complex and are incorporated in complex and diverse biological samples, which can create relevant interferences in pathogens' detection. Direct diagnostic approaches, such as microscopic examination, culture and molecular testing are carried out in equipped laboratories and require long waiting times to obtain the results. Recently developed point-of-care (POC) tests are a group of technologies that miniaturize tests into portable devices such that they can be performed both in well-equipped laboratories and outside the conventional laboratory setting. The present study aims to explore the feasibility and adaptability of newly developed platforms, with the aim of showing their versatility on different models of infectious agents: a virus (SARS-CoV2), a bacterium (*Pseudomonas aeruginosa*) and a protozoan parasite (*Leishmania infantum*). The Severe Acute Respiratory Syndrome Coronavirus 2 (SARS-CoV2) is the respiratory-transmitted virus responsible for the disease named COVID-19 that has been spreading globally since late 2019. The pandemic emergency from SARS-CoV-2 clearly showed the need for new diagnostic tests that are rapid, reliable and easy-to-use. *Pseudomonas aeruginosa* is a Gram-negative bacterium and is a major cause of infection in immunocompromised hospitalized patients. In these patients, *P.aeruginosa* causes nosocomial and ventilator-associated pneumonia as well as bacteraemia and sepsis. *P.aeruginosa* has become a major threat in the nosocomial setting because of its intrinsic resistance to several antimicrobial agents and the emergence of multi-drug resistance (MDR) strains; these factors are leading to high infection severity and increased mortality in infected patients. The management of *P. aeruginosa* infections focuses on early diagnosis and timely initiation of antimicrobial therapy. Finally, leishmaniasis is an infectious disease caused by a protozoan of the genus *Leishmania* and is one of the most prevalent parasitic diseases in the world. Clinically, there are several forms of the disease, including visceral leishmaniasis, which is fatal if not treated promptly. An increase in autochthonous cases of visceral leishmaniasis caused by *L. infantum* has recently been observed in the Emilia-Romagna region, northeastern Italy. As this is a neglected disease, resources invested in the control of this parasitic infection are scarce and diagnostic tools are often outdated and insensitive.

1.2.1.1 Outcomes (efficacy, safety) of completed and number of ongoing clinical studies utilising the same intervention in the same indication (including review of public registers)

ECLIPSE is a multicentric early feasibility study for the initial evaluation of newly developed platforms for the detection of three pathogens and has no outcomes in terms of efficacy and safety.

1.2.1.2 Level of evidence related to the mechanism of action of the intervention in the planned clinical

study population

Not applicable

1.3 Objective(s) of the clinical study (Please differentiate between primary and secondary objective(s))

The primary objective of the study is an initial evaluation (feasibility) of newly developed platforms for the detection of three selected pathogens, *i.e.*, SARS-CoV2, *P. aeruginosa*, and *L. infantum* in order to identify novel diagnostic tools that are simple to use, inexpensive, highly sensitive, and selective.

The secondary objective of the study is to evaluate the newly developed platforms using biological samples that are spiked with *P. aeruginosa* strains exhibiting different characteristics in terms of antimicrobial resistance.

1.4 Characteristics of the study population (size, age group, sex distribution, inclusion and exclusion criteria; all items with justification)

Overall, a total of 200 patients will be enrolled in the clinical study. For the retrospective phase, after obtaining informed consent, biological samples from 20 patients that tested positive for *L. infantum* at IRCCS Azienda Ospedaliero-Universitaria di Bologna (IRCCS AOUBO) will be analyzed.

In addition, samples obtained from 30 patients testing positive for SARS-CoV2 as well as 30 patients testing negative for the virus and stored in a repository by Personal Genomics (Verona) will be included. Regarding SARS-CoV2, the samples were collected during the COVID-19 pandemic emergency in routine diagnostic path. The informed consents were collected according to Guidelines 03/2020 - European Data Protection Board (EDPB); specific authorization for research use was explicitly indicated in the form (in compliance with art. 6, 1 comma, lett. a) GDPR). All the samples that will be employed in ECLIPSE activities by Personal Genomics have been completely anonymized.

For the prospective phase, patients' enrolment will be carried out at IRCCS AOUBO. We will enrol 30 patients testing positive *P. aeruginosa* and 50 negative patients for *P. aeruginosa* (including 20 *Pseudomonas*-negative patients whose respiratory samples will be used to perform bacterial spiking and/or DNA spiking); in addition, 10 Leishmania- positive and 30 Leishmania-negative patients will be enrolled.

The inclusion criteria will be as follows;

1. obtaining informed consent,
2. age \geq 18 years,
3. patients who meet one of the following conditions: positive patients for SARS-CoV2 infection (group 1), negative patients for SARS-CoV2 infection (group 2), positive patients for *P. aeruginosa* infection (group 3), negative patients for *P. aeruginosa* infection (group 4), positive patients for *L. infantum* infection (group 5), negative patients for *L. infantum* infection (group 6).

There will be no exclusion criteria.

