The study will include 6 cohorts of patients, as follows; SARS-CoV2 -positive patients (group 1), enrolled at Personal Genomics (Verona-based center) as retrospective cohort; SARS-CoV2 -negative patients (group 2), enrolled at Personal Genomics, retrospective cohort; *P. aeruginosa*-positive patients (group 3), enrolled at IRCCS AOUBO, prospective cohort; *P. aeruginosa* negative patients (group 4), enrolled at IRCCS AOUBO, prospective cohort; *L. infantum*-positive patients (group 5), enrolled at IRCCS AOUBO, retrospective and prospective cohort. Retrospective specimens will include leftover specimens collected for routine diagnostic testing, *i.e.*, archived specimens collected in the past and stored for extended periods in repositories. Samples will be obtained from patients that tested positive or negative to SARS-CoV2 (groups 1 and 2, respectively). The analyses will be carried out using the newly developed platforms at the Personal Genomics Laboratory. It should be noted that for the retrospective cohort of patients in groups 1 and 2, the patients' data have been anonymized by Personal Genomics. The retrospective phase will also involve samples obtained from patients that tested positive or negative for *L. infantum* (groups 5 and 6). Upon obtaining informed consent, an aliquot of peripheral blood samples that was previously collected according to standardized diagnostic care procedures and stored in a freezer at -80°C at the Unit of Microbiology (IRCCS AOUBO) will be used for the purpose of the study without going to affect any diagnostic investigations. The prospective phase will involve leftover samples that are obtained from standard care procedures for the diagnosis of *P. aeruginosa* or *L. infantum* infection. EDTA-peripheral blood is routinely sampled for the diagnosis of visceral leishmaniasis, while respiratory samples are routinely collected for the diagnosis of *P. aeruginosa* infection. Clinical samples will be collected for the study purposes after performing the diagnostic process and after obtaining informed consent by the enrolled patients. The leftover samples will be stored at -80°C and will be analyzed by employing the newly developed platforms provided in the study without affecting any diagnostic findings. The sample storage and analysis with the newly developed devices will be carried out at the Unit of Microbiology, IRCCS AOUBO.

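### Section 1.4 leaves no room for archived Leishmania negatives, but sections 1.5 and 3.5 use them; if 1.4 holds, 67% of positives and 0% of negatives are archived

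*Protocol*

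**What the plan says.** The Leishmania sample is described in three places in the protocol.

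- **Section 1.4 (study population).** The total is fixed: "Overall, a total of 200 patients will be enrolled in the clinical study". For the retrospective phase the only Leishmania entry is "biological samples from 20 patients that tested positive for *L. infantum* at IRCCS Azienda Ospedaliero-Universitaria di Bologna". For the prospective phase the entry is "in addition, 10 Leishmania- positive and 30 Leishmania-negative patients will be enrolled". The inclusion criteria define group 6 as the Leishmania negatives.
- **Section 1.5 (design).** The text announces "The study will include 6 cohorts of patients, as follows" and gives site and phase for five. The last entry is "L. infantum*-positive patients (group 5), enrolled at IRCCS AOUBO, retrospective and prospective cohort"; group 6 does not follow. Later in the same section: "The retrospective phase will also involve samples obtained from patients that tested positive or negative for *L. infantum* (groups 5 and 6". The next sentence describes a previously collected blood aliquot, "stored in a freezer at -80°C at the Unit of Microbiology (IRCCS AOUBO". On its face that covers both groups just named. Prospective leftovers are treated alike: "The leftover samples will be stored at -80°C and will be analyzed by employing the newly developed platforms".
- **Section 3.5 (reporting obligations).** Study-specific consent is to be obtained for archived Leishmania samples, both positive and negative.

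No section gives a number of archived Leishmania negatives.

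**The concern.** Section 1.4 has no archived negatives, while 1.5 and 3.5 rely on them. Two separate sections say so, and one arranges consent, so a single stray word does not explain it. Site staff cannot tell from the protocol whether to retrieve archived negatives and seek consent for them, or how many.

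The answer also determines what the Leishmania data can show. If 1.4 is followed, every archived Leishmania sample is positive and every negative is newly collected. A signal difference due to long storage or to the collection period could then be read as the platform telling infected from uninfected blood. The other two pathogens do not have this imbalance: both SARS-CoV2 groups are retrospective and both *P. aeruginosa* groups are prospective.

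**Working it through.** **1. Reproduce the total.** All inputs are from section 1.4.

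- Retrospective: 20 Leishmania positives + 30 SARS-CoV2 positives + 30 SARS-CoV2 negatives = 80.
- Prospective: 30 *P. aeruginosa* positives + 50 *P. aeruginosa* negatives (including the 20 for spiking) + 10 Leishmania positives + 30 Leishmania negatives = 120.
- Sum: 80 + 120 = 200, the stated total. Archived Leishmania negatives left over: 0.

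**2. If section 1.4 holds.** Archived share of positives: 20/(20 + 10) = 67%. Archived share of negatives: 0/(0 + 30) = 0%. The correlation between infection status and phase (phi) is (20 × 30 − 10 × 0)/√(30 × 30 × 20 × 40) = 600/848.5 = 0.71. The same-phase comparison is 10 positives versus 30 negatives, both prospective.

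**3. If sections 1.5 and 3.5 hold.** Let k be the number of archived negatives. The protocol gives no k, so the values below are illustrations.

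- Replacing prospective negatives, total kept at 200: phi = [20(30 − k) − 10k]/√[30 × 30 × (20 + k)(40 − k)].
- Added to the 30 prospective negatives, total 200 + k: phi = (20 × 30 − 10k)/√[30 × (30 + k)(20 + k) × 40].

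| k | Prospective negatives if replaced | Archived share of negatives | phi if replaced | Total if added | phi if added |
|---|---|---|---|---|---|
| 0 | 30 | 0% | 0.71 | 200 | 0.71 |
| 10 | 20 | 33% | 0.33 | 210 | 0.42 |
| 20 | 10 | 67% | 0.00 | 220 | 0.26 |
| 30 | 0 | 100% | −0.45 | 230 | 0.16 |

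For any k above 0, either the 30 prospective negatives or the total of 200 is misstated. Within the 200, balance is reached at k = 20. Beyond that the imbalance reverses, and at k = 30 no prospective negative remains.

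**4. Precision.** When all n samples are classified correctly, the exact (Clopper-Pearson) 95% lower limit is 0.025^(1/n): 69% for n = 10, 83% for n = 20, 88% for n = 30.

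- Best-case prospective specificity: lower limit 88% with 30 negatives, 83% with 20 and 69% with 10.
- Best-case prospective sensitivity: 10 positives, lower limit 69%, whatever k is.

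**The case against.** The strongest reply accepts the contradiction but disputes what follows from it. Five points deserve an answer.

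- **Group 6 is not without a phase.** A reader of the cohort list might infer that the protocol never says when group 6 is collected. That goes too far: section 1.5 itself names group 6 in the retrospective phase, and 1.4 has Leishmania negatives in the prospective phase. What is missing is the number in each. The gap in the list alone could be a drafting slip.
- **No pooled analysis is stated.** A reader might infer a planned 30 versus 30 comparison. The protocol says only that platform results are compared with gold-standard tests, and pooling or stratifying may be settled in a statistical analysis plan that is not shown. This stands, so the confounding is a risk for any analysis that combines the phases.
- **The confounding is partial and of unknown size.** A reader might infer that Leishmania accuracy will be biased. The document does not support that: 10 positives are prospective, both phases are kept at −80°C in the same unit, and neither storage times for Leishmania blood nor a storage effect are given.
- **The 1.4 design has a plausible reason.** Section 3.2.3 reports 20 positive blood samples in 2023 against more than 50 negative, so positives are the scarcer group. That would explain archived positives, but not why 1.5 and 3.5 describe archived negatives.
- **Moving negatives into the archive is a trade-off.** It costs prospective specificity and does nothing for prospective sensitivity. This stands too, so the split cannot be prescribed from the document.

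The early-feasibility label excuses modest precision. It does not excuse a control group whose make-up cannot be determined. Numbers by phase and archive consent are protocol matters, so an analysis plan would not cure this.

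**Conclusion.** The point holds as an internal contradiction that should be fixed. Section 1.4's counts exhaust the stated 200 without one archived Leishmania negative, while 1.5 and 3.5 say such samples are used. Nothing in the document settles which text governs. It would be wrong to conclude simply that the total of 200 is in error: it reproduces exactly, provided no archived negatives are added to the 30.

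The figures of 67% and 0% are conditional on 1.4 being the correct text. Under that reading, infection and phase are strongly but not completely associated (phi 0.71). Under the other reading the imbalance depends on a number that the protocol does not give, and at least one stated count is wrong. The consequence for accuracy estimates cannot be sized from the document.

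**What to change.** - Reconcile sections 1.4, 1.5 and 3.5 by stating the archived and prospective numbers of group 6 within the total of 200.
- Add group 6, with its site and phase, to the cohort list in 1.5.
- If archived negatives are used, as 1.5 and 3.5 say, count them within the 30 and take them from a storage period similar to that of the archived positives.
- If none are used, delete the archived-negative wording in 1.5 and 3.5.
- In either case, report Leishmania results by phase beside any combined result: prospective always, and archived where both groups exist.

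**Cost.** One protocol amendment, which section 2.2.2 requires to have prior Ethics Committee approval. Consent for archived negatives is already foreseen in 3.5. Section 1.5 on its face describes stored aliquots for both groups, but how many negatives were kept is not stated and must be confirmed. If 10 of the 30 negatives are archived, the best-case lower limit for prospective specificity falls by 5 percentage points (88% to 83%), and archived specificity becomes estimable on 10 samples. The number is for the sponsor to choose.

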1.4.1 Details on sample size and power calculation

The optimal sample size (statistical power) was chosen according to a criterion of minimizing measurement uncertainty and minimizing false positives and false negatives. Since the measurements in question involve statistical methods applied to chemical analysis (chemometrics), the criterion of optimizing the p-values associated with the statistical parameters of significance tests (in particular, t-TEST and F-TEST or ANOVA) was chosen. For example, in the case of the t-Student parameter for accuracy testing, having fixed the typical significance of analytical measurements-which is 5 percent for confidence intervals (2 sigma approach) and 0.3 percent for detection limits (3 sigma approach)-it is shown that beyond a few dozen measurements this parameter does not improve further. Therefore, in analytical chemistry we set at least 20 measurements for a calibration model and 30 measurements for direct observations. Spiking measurements will be performed to show the dependence of the signal depending on the different *Pseudomonas* strain.

1.5 Design of the clinical study (controlled / uncontrolled; randomised; open / blinded; parallel group / cross over / other, including innovative trial designs *e.g.* for personalised medicine, small study populations, or adaptive platform trials; please justify the appropriateness of the selected design)

This is an early feasibility study involving an initial evaluation of newly developed platforms for the detection of three pathogens (SARS-CoV2, *P. aeruginosa* and *L. infantum*). Furthermore, this study is retrospective and prospective, and multicentric. The results obtained by employing the newly developed

platforms will be compared with the results of gold standard tests performed according to the diagnostic care procedure.

The study will include 6 cohorts of patients, as follows; SARS-CoV2 -positive patients (group 1), enrolled at Personal Genomics (Verona-based center) as retrospective cohort; SARS-CoV2 -negative patients (group 2), enrolled at Personal Genomics, retrospective cohort; *P. aeruginosa*-positive patients (group 3), enrolled at IRCCS AOUBO, prospective cohort; *P. aeruginosa* negative patients (group 4), enrolled at IRCCS AOUBO, prospective cohort; *L. infantum*-positive patients (group 5), enrolled at IRCCS AOUBO, retrospective and prospective cohort. Retrospective specimens will include leftover specimens collected for routine diagnostic testing, *i.e.*, archived specimens collected in the past and stored for extended periods in repositories. Samples will be obtained from patients that tested positive or negative to SARS-CoV2 (groups 1 and 2, respectively). The analyses will be carried out using the newly developed platforms at the Personal Genomics Laboratory. It should be noted that for the retrospective cohort of patients in groups 1 and 2, the patients' data have been anonymized by Personal Genomics. The retrospective phase will also involve samples obtained from patients that tested positive or negative for *L. infantum* (groups 5 and 6). Upon obtaining informed consent, an aliquot of peripheral blood samples that was previously collected according to standardized diagnostic care procedures and stored in a freezer at -80°C at the Unit of Microbiology (IRCCS AOUBO) will be used for the purpose of the study without going to affect any diagnostic investigations. The prospective phase will involve leftover samples that are obtained from standard care procedures for the diagnosis of *P. aeruginosa* or *L. infantum* infection. EDTA-peripheral blood is routinely sampled for the diagnosis of visceral leishmaniasis, while respiratory samples are routinely collected for the diagnosis of *P. aeruginosa* infection. Clinical samples will be collected for the study purposes after performing the diagnostic process and after obtaining informed consent by the enrolled patients. The leftover samples will be stored at -80°C and will be analyzed by employing the newly developed platforms provided in the study without affecting any diagnostic findings. The sample storage and analysis with the newly developed devices will be carried out at the Unit of Microbiology, IRCCS AOUBO.

1.6 Type of intervention (medicinal product / advanced therapy medicinal product / medical device / *in vitro* diagnostic medical device / surgical or other invasive procedure / other medical intervention, including, *e.g.*, counselling)

Not applicable, it is not an interventional study.

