1.7 Description and timing of study procedures

In this clinical study, patients are recruited because they need to undergo diagnostic tests for presumed infection with one of the pathogens under investigation, independent of the study itself. Their diagnostic and therapeutic pathway is not altered. The patients' involvement ends with the sample collection, which is performed following the gold-standard diagnostic procedures. Only leftovers from the diagnostic care procedure will be used, and included in the study only after obtaining informed consent. The results obtained with the new platform will not affect therapeutic decisions, as the sole purpose of the study is to compare the analytical outcomes of the new platforms with those of the standard hospital procedure. No follow-up analyses are planned. The timing of the study will be as follows;

- Patients' recruitment and identification of samples.
- *P. aeruginosa* detection in the selected respiratory samples with the newly developed platforms
- Analysis of SARS-CoV-2 in the selected respiratory samples with the newly developed platforms
- Analysis of *L. infantum* in the selected peripheral blood samples with the newly developed platforms

2. Preparedness status

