3.2 Please describe how the study population will be recruited

Please give details on the recruitment strategy, monitoring of progress and potential mitigation measures

1_IRCCS AOUBO: the study population will be recruited during hospitalization. The patient will undergo sampling (peripheral blood in EDTA for diagnosis of leishmaniasis and respiratory samples for diagnosis of *P. aeruginosa* infection) during the routine diagnostic care procedures. Leftovers from the diagnostic care procedures will be selected to be included in the study only after obtaining informed consent.

2_ Personal Genomics: for SARS-CoV2 the samples were collected during the COVID-19 pandemic emergency in routine diagnostic path. All the samples that are employed in ECLIPSE activities have been completely anonymized

3.2.1 How many clinical sites will contribute to the recruitment of the study population in which countries? Are these clinical sites part of an established clinical trial network? Please also describe the selection criteria of the clinical sites.

Clinical sites are in Italy and include IRCCS AOUBO (1.1. AE) and Personal Genomics (P9) as partner of the ECLIPSE consortium.

3.2.2 Will recruitment of the study population be of competitive nature between the clinical sites?

(Please describe how underperformance of individual clinical sites in recruitment will be managed.)

Not applicable

3.2.3 What evidence supports the ability of the individual clinical sites to recruit the required number of study participants within the planned timeline (e.g. documented performance in previous clinical studies of similar complexity targeting very similar study population)?

Analysis of positive and negative clinical specimens received by IRCCS AOUBO (1.1. AE) between January 1, 2023 and December 31, 2023 was performed and the results were as follows;

- 190 bronchoalveolar lavage specimens tested positive for *P.aeruginosa* during 2023 and more than 600 samples tested *P.aeruginosa*-negative during the same period;

-20 peripheral blood samples tested positive for *L.infantum* during 2023 and more than 50 samples tested *L.infantum* negative during the same period.

This evaluation clearly displays the ability of IRCCS AOUBO (1.1. AE) to recruit the requested number of study participants and the related clinical samples.

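### Does leaving the respiratory specimen type open for the P. aeruginosa groups bias the comparison of positives with negatives?

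*Protocol*

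**What the plan says.** Section 1.4 sets the P. aeruginosa quotas: "We will enrol 30 patients testing positive *P. aeruginosa* and 50 negative patients for *P. aeruginosa", with 20 of the negatives reserved for spiking. Eligibility for groups 3 and 4 rests on infection status, consent and age, and "There will be no exclusion criteria".

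The specimen is described only as respiratory. Section 1.5 states that "respiratory samples are routinely collected for the diagnosis of *P. aeruginosa* infection", section 1.7 speaks of "detection in the selected respiratory samples with the newly developed platforms", and section 3.2 uses the same general term. Section 1.7 implies that samples are selected but gives no criterion.

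Lavage is named once, in the 2023 count of section 3.2.3: "190 bronchoalveolar lavage specimens tested positive for *P.aeruginosa* during 2023 and more than 600 samples tested" negative. The matching Leishmania line reads "20 peripheral blood samples tested positive for *L.infantum* during 2023 and more than 50 samples tested *L.infantum* negative". Both counts are offered as evidence that the hospital is able "to recruit the requested number of study participants and the related clinical samples".

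**The concern.** Positives and negatives are recruited to separate quotas, so the specimen mix in each group depends on who is picked. Section 1.2.1 itself says that complex and diverse sample material can interfere with detection. If positives were mostly one kind of respiratory specimen and negatives mostly another, a platform that responded partly to the material could appear to separate infected from uninfected patients. A shift in the opposite direction could hide a real signal. The 20 spiking negatives raise the same question, because their material is not named either.

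Sample choice is settled at enrolment. A later analysis can adjust for specimen type only if type was recorded, and adjustment fails if each group has its own type. For Leishmania the protocol does name one material for both groups (EDTA peripheral blood), so the contrast within section 1.5 is visible.

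**Working it through.** **1. What the text supports.** Three readings are possible.

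- *Lavage in both groups.* Section 3.2.3 names lavage for the 190 positives and calls the 600 or more negatives simply samples. The Leishmania line is shortened in the same way, and there the negatives are plainly blood as well. This reading is probable but not certain. It gives no confounding.
- *Several respiratory types in similar proportions.* This also gives no confounding, only some added variance.
- *Several types in different proportions.* Only this reading causes bias. The text does not rule it out, and nothing in it shows that it will happen.

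**2. Availability if lavage is meant.** Positives: 30/190 = 15.8% of the 2023 count. Negatives: 50/600 = 8.3%, if those samples are lavage. Supply would not push recruiters towards other specimens.

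**3. Size under the third reading.** The protocol gives no figure to reproduce here. Let s be the signal shift between two specimen types, in within-type SD, and let p and q be the share of the shifted type in positives and negatives.

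- Bias in the mean difference = s × (p − q). With s = 1, p = 0.8 and q = 0.4 it is 0.4 SD. With s = 0.5 it is 0.2 SD. With p = q it is 0.
- AUC with no true signal = 0.5 × [pq + (1−p)(1−q)] + p(1−q) × Φ(s/√2) + (1−p)q × Φ(−s/√2). At 80/40 and s = 1: 0.5 × 0.44 + 0.48 × 0.760 + 0.08 × 0.240 = 0.604.

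The table shows a simulated two-sided 5% t-test, 30 v 30 (50 negatives less 20 for spiking), with normal signals and 200,000 runs. Each pair is s = 0.5 / s = 1. Every value of s, p and q, and the true signal of 0.8 SD, is an assumption.

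| Mix p/q | False significance | AUC, no true signal | Power, true 0.8 SD, opposing shift | Power with type factor |
|---|---|---|---|---|
| 40/40 | 4.4% / 2.9% | 0.500 / 0.500 | 84.7% / 80.3% | 86% |
| 60/40 | 6.0% / 7.8% | 0.528 / 0.552 | 74.0% / 53.7% | 85% |
| 70/40 | 7.9% / 15.1% | 0.541 / 0.578 | 67.8% / 39.3% | 83% |
| 80/40 | 10.8% / 26.6% | 0.555 / 0.604 | 61.0% / 26.4% | 79% |

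With the type factor, the error rate is 5.0% to 5.1% throughout. Balancing the mix as well would add at most 86 − 79 = 7 points of power.

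**4. Dependence on the assumed signal.** A 0.8 SD signal corresponds to AUC = Φ(0.8/√2) = 0.71, which is weak for a detection platform. With an assumed signal of 2 SD and the worst case above (80/40, opposing 1 SD shift), AUC = 0.44 × 0.921 + 0.48 × 0.760 + 0.08 × 0.983 = 0.85, against 0.90 at equal mixes. With 3 SD it is 0.95 against 0.97. Power of the t-test stays at about 100% in both. The large losses in the table therefore belong to a weak signal.

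**The case for a change.** The strongest case for a change is that specimen eligibility belongs in the protocol, that a feasibility count binds no recruiter, and that one sentence would settle the matter without another patient. Section 1.7 makes comparison with the hospital's standard procedure the sole purpose of the study, so an avoidable confounder deserves attention even at this early stage. In a harsher scenario the figures grow: if every positive is lavage, half the negatives are another type and the platform does not respond to the pathogen at all, the chance of a significant difference in the direction of the shift is 16% to 45% with 30 v 30, against a nominal 2.5%.

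The factual part stands: no specimen rule is stated. The standard operating procedures promised in section 2.2.1 are to cover sampling, but they are not yet written and no rule can be read into them. The harmonisation promised in section 3.4 concerns data, not specimens.

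The inference of harm does not stand. The harsher scenario needs three conditions, none of them documented. Both P. aeruginosa groups are inpatients of one hospital, tested for presumed infection on the same routine pathway and analysed in one unit. That does not guarantee equal mixes, but it gives no support to the case where each group has its own type. The absence of exclusion criteria concerns patients and does not direct which specimens are chosen.

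**Conclusion.** No change follows. The protocol leaves a descriptive detail unstated, but no stated rule, number or analysis is shown to give a wrong result. On the most likely reading (lavage in both groups) the bias is zero, as it is for any equal mix. Under unequal mixes the size is unknown. The illustrative 6% to 27% false significance (60/40 to 80/40, 30 v 30) rests entirely on assumed shifts and shares, and is not evidence of harm in this study. If several types are used, recording type and fitting it as a factor holds the error at 5% and power at 79% to 86% over the mixes examined. Those are ordinary choices for laboratory procedures and an analysis plan.

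The conclusion rests on two assumptions: the laboratory knows and records which specimen it stores, and the two groups do not come from entirely separate specimen types. If the second failed, no adjustment would help. Nothing in the protocol suggests that it will. Section 1.7 also confirms that platform results do not influence treatment.
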